9.4. Statistical Analysis

9.4.1. Sequence of Analysis

Two analyses will be conducted: the primary analysis after all participants have reached the Day 28 follow up, and a follow-up analysis at the end of the 6 months follow-up.

- The primary analysis will be performed when efficacy and safety clean data up to and including the study Day 28 visit are available from all participants. Before this analysis, the blinded data review will be conducted, the final SAP will be signed, and a formal database lock will take place. The list of study personnel with access to the result will be appropriately documented prior to unblinding. Appropriately defined study personnel will remain blinded (i.e., will not have access to the individual participant treatment assignment) until end of follow-up and final database lock. No individual listings mentioning individual participant treatment assignment will be released to the remaining study personnel until End of Study (EOS) and the Investigator will not have access to the treatment allocation up to study end and final database lock. The main analysis will be considered as final for key efficacy endpoints.
- The final EOS analysis will be performed when all endpoint data (safety and efficacy) up to study follow-up end (Month 6) are available and locked. All tertiary endpoints available at that time may also be analysed in this step. An integrated CSR containing all data will be written and made available to the sponsor and the Investigator. Individual listings will only be provided at this stage.

The SAP will provide a detailed description of the analyses that will be computed at the time of each analysis.

The final CSR will contain at least the final analyses of endpoints. If the data for tertiary endpoints become available at a later stage, (an) additional analysis/analyses may be performed. These analyses may be documented separately to the CSR and may be made available to the Sponsor and Investigators at that time.

9.5. Statistical Analysis Plan

Data will be analysed and reported using SAS® version 9.4 or later.

hVIVO template identifier: (G_0687) v3.0

Primary and secondary efficacy endpoints will be descriptively summarised. Continuous variables will be summarised using a number of observations, mean (and/or geometric mean, where applicable), standard deviation, standard error, median, lower quartile, upper quartile, minimum and maximum values. Categorical variables will be summarised using proportions (counts and percentages).

Statistical analyses for the primary endpoint will be performed using appropriate one or two-sided hypothesis tests at the 5% significance level, with further details in the SAP. The t-test will be used to compare means between groups (and/or an appropriate alternative test, e.g. Wilcoxon Rank-Sum test, if the t-test assumptions are not satisfied). Methods for checking statistical model assumptions will be described in the SAP. Dichotomous data will be tested using a chi-squared test. No adjustment for the type I error is planned, as this is an early stage exploratory study.

The detailed SAP will be developed by S-cubed and approved by the Sponsor prior to any look at unblinded data. The SAP will give a more detailed description of the report presentations to be produced for the study expanding on the protocol specified analysis. Any deviation(s) from the original statistical plan should be described and justified in an amendment to the protocol and/or SAP as appropriate and referenced also in the final clinical study report (CSR). The SAP will describe and account for the occurrence of and extent of missing data, and its possible impact on the study analysis. All baseline assessments will be described in the SAP.

Further post-hoc evaluations of any exploratory endpoints may be conducted and reported separately.

9.6. General Considerations

9.6.1. Participant Accountability

The number of participants receiving RSVpreF or placebo, receiving Challenge Virus, withdrawing from study (also split by reason for withdrawal), and completing the study, and the numbers in each analysis set, will be summarised.

9.6.2. Protocol Deviations

Participants data will be reviewed for major protocol deviations prior to main analysis database lock at a planned blinded data review meeting (BDRM), and decisions will be documented within the meeting minutes. At this meeting, participants will be reviewed for their inclusion/exclusion from the analysis sets.

9.6.3. Demographic and Baseline Characteristics

Descriptive statistics of demographics (age, sex, height, weight, BMI, and ethnicity) will be presented by treatment group and across all participants. Medical history information will be listed. Other baseline characteristics will be defined in the SAP.

9.6.4. Compliance to Study Treatment

Compliance with study vaccine will be computed for each group as proportion of subjects received vaccine as randomised.

9.6.5. Primary Efficacy Analysis

The primary efficacy analysis of the primary endpoint family (as specified below) will be performed on the ITTc Analysis Set.

- The AUC for RSV-A Memphis 37b viral load measured in nasal samples by RT-qPCR, as determined by qRT-PCR on nasal samples collected twice daily starting two days post-viral challenge (Day +2) up to discharge from quarantine, will be summarised and RSVpreF compared to placebo via a t-test or Wilcoxon Rank-Sum test as appropriate.
- Symptomatic RSV infections will be summarised and RSVpreF compared to placebo using a chi-squared test. RT-PCR-confirmed symptomatic RSV infection, defined as:
 - RT-PCR-confirmed RSV infection (two detectable qRT-PCR measurements (reported on 2 or more consecutive days), starting two days post-viral challenge (Day +2) up to discharge from quarantine.), AND
 - Either one or more positive clinical symptoms of any grade from two different categories in the symptom scoring system (Upper Respiratory, Lower Respiratory, Systemic), or one Grade 2 symptom from any category.
- Sum total symptoms, as measured by graded symptom scoring system collected three times daily starting one days post-viral challenge (Day +1) up to discharge from quarantine, will be summarised and RSVpreF compared to placebo using a t-test or Wilcoxon Rank-Sum test as appropriate.

The primary efficacy analysis will be supported by sensitivity analyses and these will be specified in the SAP.

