Safety Assessments																									
Solicited AE recording (k)	X	←	→																						
Unsolicited AE recording (l)		←	→																						
Medically Attended AEs (MAEs) and SAE recording		←	→																						
Concomitant medications	X	←	→																						

KEY NOTES FOR SCHEDULE OF EVENTS

hVIVO template identifier: (G_0687) v3.0

X	Once
BD	Twice Daily, 12 hours between assessments (\pm 1 hour).
TDS	Three Times Daily, at the same time each day (\pm 1 hour).
T	To determine tolerance of the procedure only (sample will not be tested).
*	All screening assessments will be performed under hVIVO Generic Screening process. Results of tests or examinations performed under hVIVO Generic Screening process, and from Day -118 (Day -118 for viral serology and Day-84 for other assessments including safety laboratory test) prior to vaccination may be used to determine eligibility without the need to repeat the assessment following study specific consent.
+	Only the applicable Inclusion/Exclusion criteria will be reviewed at each time point.
#	Admission can occur on Day -2 or Day -1 and therefore procedures can be performed on Day-2 or Day-1. If admission is on Day -1 then those procedures which occur on both Day -2 and -1 will only be captured using the timepoints of Day -1. For TDS assessments on Day -2/Day-1: When Quarantine Admission occurs on Day -1, assessments will be performed up to three times daily.
a	Study-specific consent may occur on the day of vaccination, providing all required eligibility information has been collected through the hVIVO generic screening process.
b	Height will be taken at Screening only.
c	Distribution of paper tissues and bags will start on Day -1, with the first collection on Day 0. Thereafter collection of tissues will occur at the same timepoints (\pm 1 hour) with tissues distributed 24h ahead.
d	Assessments will be performed at the same time each day during quarantine (\pm 1 hour).
e	Blood will be drawn under non-fasted conditions. Repeat bloods may be drawn under fasted conditions if a lipid profile (triglyceride) or glucose is required (at PI discretion).
f	Vaccine and viral challenge serology (e.g. RSV neutralisation antibody assay) will be performed to determine eligibility and seroconversion. Non-vaccine antigen-binding antibody assay will be used for serological detection/seroconversion of community acquired RSV infection between vaccination and viral challenge.

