
 To evaluate the safety and reactogenicity of RSVpreF, when compared to placebo 	
To evaluate the incidence of the following endpoints:
 
 Occurrence of solicited local reactions and systemic events within 7 days (i.e., on the day of vaccination and 6 subsequent days) after vaccination. Occurrence of unsolicited adverse events (AEs) within 30 days (i.e., on the day of vaccination and 29 subsequent days) after vaccination Occurrence of medically attended AEs (MAEs) and serious adverse events (SAEs) from vaccination (Day -28) up to study end (Day +155).

 To evaluate the safety of the RSV challenge model. 	
To list the incidence of the following endpoints:
 
 Occurrence of unsolicited AEs within 30 days post-viral challenge (Day 0) up to Day +28 follow up. Occurrence of SAEs related to the viral challenge from the viral challenge (Day 0) up to Day +28 follow up. Occurrence of haematological and biochemical laboratory abnormalities during the quarantine period. Use of concomitant medications within 30 days post-viral challenge (Day 0 up to Day +28 follow up).
TERTIARY	
Tertiary/exploratory endpoints include but are not limited to the following.	

 To evaluate the effect of baseline immune status on immunogenicity and efficacy of the RSVpreF, when compared to placebo 	
 The primary, secondary, and tertiary endpoints may be explored in relation to the baseline status of participants and the response to vaccination.

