8.15.2. Challenge Virus Serology Samples

A participant must be sero-suitable to take part in the study; i.e. he/she must have low pre-existing serum levels of antibodies specific to the Challenge Virus. This antibody titer cut-off for serosuitability will be described in the AP.

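### The three primary comparisons ignore the pre-vaccination RSV antibody titre that every participant must have to enter; adjusting for it would be a cheap, modest gain in precision

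*Combined protocol and SAP*

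**What the plan says.** Section 9.6.5 sets out the primary comparisons on the ITTc set. VL-AUC "will be summarised and RSVpreF compared to placebo via a t-test or Wilcoxon Rank-Sum test as appropriate". The sum total symptom score "will be summarised and RSVpreF compared to placebo using a t-test or Wilcoxon Rank-Sum test as appropriate". For symptomatic infection Section 9.5 is definite: "Dichotomous data will be tested using a chi-squared test". Sections 9.5 and 9.6 name no covariate, and Section 6.3 names no stratification factor.

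Section 9.5 allows an alternative to the t-test, with Wilcoxon as the example, "if the t-test assumptions are not satisfied". It adds: "Methods for checking statistical model assumptions will be described in the SAP". That SAP is a separate document, not part of the material reviewed. It is to be approved before anyone sees unblinded data (Section 9.5) and signed before the lock for the Day 28 analysis (Section 9.4.1).

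On serology, Section 8.15.2 says that to be sero-suitable "he/she must have low pre-existing serum levels of antibodies specific to the Challenge Virus". Key note f to the schedule in Section 1.3 says: "Vaccine and viral challenge serology (e.g. RSV neutralisation antibody assay) will be performed to determine eligibility and seroconversion". The schedule marks the humoral-immunity serum sample, without the parentheses that denote optional items, at screening and at the vaccination visit. Baseline immunity appears in the objectives only at the tertiary level: "To evaluate the effect of baseline immune status on immunogenicity and efficacy of the RSVpreF, when compared to placebo".

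**The concern.** The protocol treats pre-existing antibody as a determinant of whether challenge takes: entry is restricted on it, and a tertiary objective asks how it modifies efficacy. A variable that predicts outcome and is measured before randomised treatment is the standard candidate for covariate adjustment. Leaving it out has two consequences in a trial of 31 per arm.

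- Outcome variation explained by baseline titre stays in the error term. VL-AUC, the endpoint that drives the sample size, has almost no power to spare.
- A chance difference in baseline titre between the arms is not corrected. The standard error of that difference is √(2/31) = 0.25 titre SDs, so roughly one trial in three would show a gap above 0.25 SD and one in twenty a gap above 0.5 SD.

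**Working it through.** **Inputs (Section 9.2).** 31 per arm. VL-AUC: 70% reduction, CV 96%, two-sided 5%. Symptom sum: 80% reduction, common CV 113.55%, one-sided 5%. Symptomatic infection: 59.26% against 23.7%, two-sided 5%. The within-arm correlation r between log baseline titre and outcome is an assumption, because the documents give none. I show r from 0 to 0.4.

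**Reproducing the plan.** Take the SD as CV × control mean, common to both arms.

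- VL-AUC: d = 0.70/0.96 = 0.729; noncentrality = 0.729 × √(31/2) = 2.87; 60 df. Exact t power is 80.6% at 31 per arm and 79.3% at 30. This matches the stated 80%.
- Symptom sum: d = 0.80/1.1355 = 0.705; noncentrality = 2.77. One-sided power is 86.4%, consistent with at least 80%.
- Symptomatic infection: the pooled two-proportion formula gives 29 per arm, and 82.8% power at 31 (exact chi-squared 83.7%).

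The plan's sample size therefore stands with unadjusted tests.

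**Adding the covariate.** In a linear model on arm and log titre, the variance of the arm effect becomes (2/n) × (1 − r²) × [1 + 1/(2n − 4)] in units of the outcome variance, with 2n − 3 = 59 df. The bracket, 1 + 1/58, is the average price of chance imbalance.

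| r | 1 − r² | VL-AUC, two-sided | Symptom sum, one-sided |
|---|---|---|---|
| unadjusted | – | 80.6% | 86.4% |
| 0 | 1.00 | 80.0% | 85.9% |
| 0.1 | 0.99 | 80.3% | 86.2% |
| 0.2 | 0.96 | 81.5% | 87.1% |
| 0.3 | 0.91 | 83.5% | 88.6% |
| 0.4 | 0.84 | 86.3% | 90.7% |

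Break-even is near (1 − r²)(1 + 1/58) = 1, that is r² = 1/59 or r ≈ 0.13, ignoring the one lost degree of freedom.

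**Symptomatic infection.** This was simulated with 20,000 trials per value of r, a latent normal outcome and an adjusted risk difference. Adjusted against chi-squared power was 82.9% against 83.8% at r = 0, 83.3% against 83.3% at 0.2, 84.8% against 83.8% at 0.3, and 86.3% against 83.7% at 0.4. In the null runs at r = 0 to 0.4, the adjusted test rejected in 4.8–5.3% of trials.

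**Effect of the entry restriction.** If restricting entry cuts the titre SD to a fraction u of its unrestricted value, r becomes ru/√(1 − r² + r²u²). An unrestricted 0.4 falls to 0.31 at u = 0.75 and 0.21 at u = 0.50. This points to the r = 0.2 and 0.3 rows: a VL-AUC gain of 0.9 to 2.9 points.

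**The case against.** **The gain is small and assumed.** This stands. No correlation is given, low-titre entry narrows the covariate, and vaccine-induced antibody may weaken the link with baseline titre in the RSVpreF arm. The trial is also described as exploratory.

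**A linear model on means may be the wrong scale.** This stands too, and it shapes the fix. Zero-inflated gamma data were simulated to match the VL-AUC CV, with an assumed 20% zeros in controls and a 50% reduction. When the vaccine acted by preventing infection, Wilcoxon had 82% power against 58% for the t-test. When it scaled the values down, the order reversed. The choice of scale can matter more than the covariate.

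**The assay may not be ready.** Post-enrolment humoral assays are listed as possible, not committed (Sections 3 and 8.15.3), and tertiary data may arrive after the Day 28 analysis (Section 9.4.1). Only the screening value is assured, and it may date from Day -118, up to 90 days before the Day -28 vaccination.

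**A reader might infer that the t-or-Wilcoxon choice inflates type I error.** The documents do not show this. Section 9.5 ties the choice to an assumption check and puts the method in an SAP approved before unblinding. In simulated null trials, a fixed rule (Shapiro-Wilk, then t or Wilcoxon) held 4.8–5.0%. Error rose to 5.8–6.8% only when the smaller of the two p-values was taken, a procedure the plan does not describe. The chi-squared test is fixed in any case.

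**A reader might also infer that the symptom score is underpowered.** It would have 77.9% power if tested two-sided, but Section 9.2 powers it one-sided, where it has 86.4%.

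**Conclusion.** The point holds as an efficiency improvement. The primary comparisons leave out a baseline variable that the protocol regards as relevant to susceptibility and obtains for everyone.

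The VL-AUC gain of 0.9 to 5.7 points at r = 0.2 to 0.4 is more likely 1 to 3 points after the low-titre restriction. The symptom sum gains 0.7 to 4.3 points, one-sided. Symptomatic infection gains about 1 to 3 points at r = 0.3 to 0.4 and nothing at 0.2. The worst case, an uninformative titre, costs 0.5 to 0.9 points. These figures assume the plan's CVs and effects, a common r in both arms and, for the continuous endpoints, equal-variance normal errors.

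Nothing here makes the unadjusted analyses invalid. The SAP may already contain an adjusted sensitivity analysis; the documents neither show nor exclude it.

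**What to change.** Before unblinding, state in the SAP that the primary comparisons adjust for log baseline RSV titre.

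- **Covariate.** Use the screening eligibility value for all participants. Use the Day -28 pre-dose value instead only if that assay is committed to before the Day 28 analysis. State how values below the assay limit are handled.
- **VL-AUC and symptom sum.** Choose the scale for each endpoint in advance. On the mean scale, use a linear model on arm and log titre with robust or re-randomisation inference. If a rank analysis is chosen, use rank-based ANCOVA.
- **Symptomatic infection.** Report a covariate-standardised risk difference with its confidence interval.
- **Supportive.** Keep the t, Wilcoxon and chi-squared tests.

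The cost is some SAP text and a few lines of code, with no new samples or visits. The statistical price is under one power point if the titre proves uninformative. The operational condition is that the chosen titre is in the database by the Day 28 lock.

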9.6.6. Secondary Efficacy Analysis

Secondary endpoints as described in [Section 3](#) will be summarised by treatment group and analysed per Section 9.5 as appropriate.

9.6.7. Tertiary/exploratory Analysis

Except if otherwise specified, no formal statistical testing will be conducted for tertiary endpoints described in [Section 3](#). Only the descriptive statistics will be computed. These analyses will be described in the SAP.

9.6.8. Safety Analyse(s)

Safety data will be summarised descriptively.

AEs will be coded using the most current version of the Medical Dictionary for Regulatory Activities (MedDRA) and summarised by system organ class, preferred term, and treatment group for the number of AEs reported and the number and percentage of participants reporting each AE.

Solicited local and systemic AEs and unsolicited AEs will be summarised descriptively.

A by-participant AE data listing including onset and resolution dates, verbatim term, preferred term, blinded treatment, severity, relationship to treatment, action taken, and outcome will be provided.

Other safety endpoints will be presented by treatment group includes laboratory evaluations (biochemistry, haematology, coagulation (if required), cardiac enzymes and urine analysis), vital signs assessments, physical examinations, 12-lead ECG and Spirometry. Additionally, physical examinations will be listed.

9.6.9. Other Analyse(s)

Certain pre-specified primary and secondary analysis (as documented in the SAP) will also be performed for the “Lab-confirmed infected” subgroup. The subgroup is defined as those participants that fulfil the following criteria:

- RT-PCR-confirmed quantifiable infection (two quantifiable RT-PCR measurements (reported on 2 or more consecutive days), starting two days post-viral challenge (Day +2) up to discharge from quarantine)

9.7. Interim Analyses

No interim analysis (i.e. an analysis of early trial data, before enrolment is completed, to detect trends that might warrant modification of the protocol, change in data being collected or trial termination) is planned for the study. A sequence of two analyses (primary analyses after the study Day 28 visit, and an EOS analysis after last participant last scheduled visit) is planned and described in [Section 9.4.1](#).

The infection rate in the placebo group will be monitored on an ongoing basis by an unblinded statistician who does not have any other study function to confirm the powering assumptions (i.e. infection rate) within the Placebo group and ensure sufficient infection rate has occurred. If the infection rate is lower than anticipated, additional participants (up to 5 per treatment group) may be enrolled if needed to ensure the study is not underpowered.

The unblinded statistician will also monitor participant drop out between vaccination and inoculation to confirm that the number of participants inoculated in each treatment group is balance and 31 evaluable participants in each treatment group is achieved when the study is complete.

10. Supporting Documentation and Operational Considerations

10.1. Appendix 1: Regulatory, Ethical, and Study Oversight Considerations

10.1.1. Regulatory and Ethical Considerations

This study will be conducted in accordance with the protocol and with the following:

- Consensus ethical principles derived from international guidelines including the Declaration of Helsinki and Council for International Organizations of Medical Sciences (CIOMS) International Ethical Guidelines
- Applicable ICH Good Clinical Practice (GCP) Guidelines
- Applicable laws and regulations

In addition to regulatory submission, the protocol, protocol amendments, ICF, Investigator Brochure, and other relevant documents (e.g., advertisements) must be submitted to a REC by the Investigator and reviewed and approved by the REC before the study is initiated.

Substantial amendments to the protocol will require Regulatory Authority approval prior to implementation. Any amendments to the protocol will require REC approval before implementation of changes made to the study design, except for changes necessary to eliminate an immediate hazard to study participants.

The Investigator will be responsible for the following:

- Providing written summaries of the status of the study to the REC annually or more frequently in accordance with the requirements, policies, and procedures established by the REC
- Notifying the REC of SAEs or other significant safety findings as required by REC procedures
- Providing oversight of the conduct of the study at the site and adherence to requirements of ICH guidelines, the REC, European regulation 536/2014 for clinical studies (if applicable), and all other applicable local regulations

10.1.2. Financial Disclosure

Investigators and sub-Investigators will provide the Sponsor with sufficient, accurate financial information as requested to allow the Sponsor to submit complete and accurate financial certification or disclosure statements to the appropriate regulatory authorities. Investigators are responsible for providing information on financial interests during the course of the study.

